#### 5.2.2 Analysis of secondary endpoint

The secondary outcomes are health care use (e.g., visiting a doctor, medication), direct and indirect costs, depression severity after one and 12 months (PHQ-9), diagnosis of depressive disorder according to MINI structured interview, anxiety (GAD-7), somatic symptom severity (SSS-8) and quality-adjusted life years (QALYs). Secondary endpoints will be analysed with the data collected in the 1-month, 6-month, and 12-months follow-up like the primary endpoint. Adjusted and non-adjusted means, effect sizes (Cohen's d) and confidence intervals will be reported.

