## 1.2 Objectives

This trial is conducted to primarily determine the efficacy of a widely available feedback intervention after depression screening for depressive symptomology in six months as well as costs, depression severity after 1 and 12 months, diagnosis of depression (MINI), anxiety (GAD-7), somatic symptom severity (SSS-8) and quality-adjusted life years as secondary endpoints. Primary hypothesis: patient-oriented electronic depression feedback (including GP feedback) leads to a lower depression severity (PHQ-9) after 6 months compared to both GP feedback and no feedback at all. Secondary hypothesis: patient-oriented feedback after depression screening is more cost efficient after 6 months compared to both GP feedback and no feedback at all caused by a reduction of health costs (CSSRI). Furthermore, the influence

of Germany's first implementation of a depression screening on routine care of primary medical patients is evaluated.

The primary and secondary endpoints are in detail (Table 1 in the approval):

Instruments	Measurement			
	Baseline	1-month follow-up	6-months follow-up	12-months follow-up
Primary Endpoint				
Depression severity (PHQ-9)	x	x	x	x
Secondary Endpoint				
Clinical scales (Anxiety severity, GAD-7, somatic symptom severity, SSS-8, quality of life, EQ5D)	x	x	x	x
Patient knowledge and behavior regarding guideline recommendations (e.g., adherence, coping, search for information)			x	x
Health care use (e.g., doctor consultations, medication) (CSSRI)			x	x
Mini-International Neuropsychiatric Interview (MINI)		x	x	x
Patient activation (PAM13-D)			x	
Satisfaction and acceptance of screening and feedback (USE)			x	
Open questions (e.g., strategies in response to a diagnosis)				x
Medical record (i. e., diagnosis, treatment)	x		x	
Demographic information	x			

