### 2.2 Randomization

A randomising sequence is created (boxes for 97 patients with probabilities for each condition derived from estimated prevalences and two test entries – 999 total boxes) not being SAP **2.0**

accessible for neither study nurse nor GP at any given point. After a patient has finished the baseline measurement, reached a PHQ-9 score higher than 9, randomisation happens electronically (allocation concealment). Patients are stratified by their depression severity (moderate and severe). The study is not cluster-randomised, as within every single GP's office each of the three conditions is realised and therefore an individual randomisation of patients is feasible.

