### 5.2 Analysis methods

#### 5.2.1 Analysis of primary endpoint

The primary outcome of all randomised patients will be analysed regarding the intention-to-treat principle and according to the memorandum of the DFG about good clinical practice all study results are going to be documented and published.

Primary outcome: depression severity (PHQ-9 score) 6 months after intervention as change from baseline. The primary outcome is going to be analysed via a mixed effects model including random effects patients and GP practices nested in centres and fixed factors for group and depression severity. The baseline comparisons will be represented by statistical contrasts. The use of the closure test ensures a familywise significance level of 5% if the p-value of the overall test is below 0.05.

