#### 5.2.3 Additional analysis

As additional exploratory analyses, subgroup analyses based on several demographic and clinical values are conducted w.r.t. change of PHQ-9 score. The aim of these analyses is to identify subpopulations, which benefit more or less from the intervention. These analyses shall give a first starting point for future studies. Missing values will not be imputed, but the implicit MAR assumption of the analysis model will be used.

The presented p-values are of descriptive nature only (two-sided tests at unadjusted significance level of 5%). The analyses are conducted in the FAS.

For the analyses on a potential interaction between the intervention and age (continuous, and categorical: young [ $\leq$ first tercile] vs. old [ $>$ third tercile]), sex (men vs. woman), depression history (previous episode vs. no history of depression), other mental health comorbidity (mental health comorbidity vs. mental health comorbidity), city size (ordinal), education ( $\leq$  10 years in school vs.  $>$  10 years in school), living situation (living together vs. alone), insurance status (private vs. statutory health insurance), reason for GP visit (psychological vs. physical), migration background (migration background vs. no migration background), quality of life at baseline (continuous and dichotomized with median as cut-off point; based on the visual analogue scale of the EQ-5D), anxiety disorder (yes vs. no), substance disorder (yes vs. no), chronic physical disease (yes vs. no), persistent somatic symptoms (yes vs. no), mood swings (yes vs. no), social support (yes vs no), pregnancy in female patients (yes vs. no) and breast feeding in female patients (yes vs. no) on the change in PHQ-9 score from baseline to month 6, the regression models and their parameters are defined analogously to the primary analyses but additional effects for demographic and clinical values and its interaction with the treatment are added to each model.

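### The stated QALY model (SAP 5.2.2) leaves out baseline EQ-5D utility, which the trial collects: precision is lost and part of any realised baseline imbalance carries into the QALY difference

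*SAP*

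**What the plan says.** Section 5.2.2 of the SAP includes QALYs among the secondary outcomes and gives one analysis rule for all of them: "Secondary endpoints will be analysed with the data collected in the 1-month, 6-month, and 12-months follow-up like the primary endpoint". Its last sentence promises both adjusted and unadjusted means but does not name the adjustment variables.

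Section 5.2.1 defines the template. The outcome is "depression severity (PHQ-9 score) 6 months after intervention as change from baseline", and the mixed model has "random effects patients and GP practices nested in centres and fixed factors for group and depression severity". Section 2.2 shows what the severity factor is: "Patients are stratified by their depression severity (moderate and severe"). It is the two-level PHQ-9 randomisation stratum.

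The endpoint table in section 1.2 has a row "Clinical scales (Anxiety severity, GAD-7, somatic symptom severity, SSS-8, quality of life, EQ5D") marked at baseline, 1, 6 and 12 months. The only analysis use that the SAP states for the baseline EQ-5D is in section 5.2.3, as an exploratory subgroup variable for PHQ-9 change: "quality of life at baseline (continuous and dichotomized with median as cut-off point; based on the visual analogue scale of the EQ-5D").

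Section 1.2 also states a secondary hypothesis that "patient-oriented feedback after depression screening is more cost efficient after 6 months compared to both GP feedback and no feedback at all".

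**The concern.** The primary template handles the baseline of its own instrument by analysing a change score. GAD-7 and SSS-8, which are measured at baseline, can inherit that. A QALY in its usual form cannot. It is an area under the utility curve over a period, it has no baseline value of its own to subtract, and baseline utility is its first point. A chance difference between arms in starting utility therefore enters the QALY difference directly through that point, and indirectly because later utilities correlate with the first. The severity stratum absorbs some of this, but it is a two-category split on a different instrument.

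At stake is the precision of the QALY comparison. If QALYs are the effect measure for the cost-efficiency hypothesis, the effect side of that comparison is also at stake.

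**Working it through.** **The plan's own figure.** Section 2.3 plans 233 per group for a three-group F-test with group effects 0, 0 and 0.25 SD. The noncentrality is 233 × (2/3) × 0.25² = 9.71 on 2 and 696 degrees of freedom, which gives power 0.801 at the 5% level. The 233 reproduces and is not in dispute. It is used below as the number per arm at 6 months.

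**Assumptions (none is in the SAP).**
- The QALY is a trapezoid area over months 0, 1 and 6.
- Utility has the same SD at each visit (taken as 1), with equal correlation ρ between visits, ρ = 0.3 to 0.7.
- Severity correlates s = 0.5 with baseline utility and relates to later utility only through it.
- The QALY effect is 0.25 of the QALY's raw SD, borrowed from the PHQ-9 effect in section 2.3.

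**Weights (years).** Month 0: 1/24 = 0.0417. Month 1: 1/24 + 5/24 = 0.25. Month 6: 5/24 = 0.2083. The sum is 0.5 and the sum of squares is 0.1076.

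**Formulas.**
- QALY variance: V = (1 − ρ) × 0.1076 + ρ × 0.5²
- Slope of the QALY on baseline utility: b = 0.0417 + ρ × 0.4583
- Residual variance with severity only (the stated model): V − s²b²
- Residual variance with baseline utility added: V − b²
- Pairwise noncentrality: 0.25 × √V / √(residual variance) × √(233/2)
- Carry-over for a one-standard-error imbalance in baseline utility given severity, as a share of the effect: b × √(1 − s²) × √(2/233) / (0.25 × √V)

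**At ρ = 0.5.** V = 0.0538 + 0.125 = 0.1788 and b = 0.2708.
- Residual variance falls from 0.1788 − 0.25 × 0.0733 = 0.1605 to 0.1788 − 0.0733 = 0.1055, a cut of 34%.
- Noncentrality rises from 2.85 to 3.51, and two-sided 5% power from about 81% to 94%.
- Carry-over is 0.2708 × 0.866 × 0.0926 / 0.1057 = 21%.

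**Over the range.**

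| ρ | V | b | Variance cut | Power, stated model | Power with baseline utility | Carry-over removed |
|---|---|---|---|---|---|---|
| 0.3 | 0.1503 | 0.1792 | 17% | 79% | 86% | 15% |
| 0.5 | 0.1788 | 0.2708 | 34% | 81% | 94% | 21% |
| 0.7 | 0.2073 | 0.3625 | 57% | 84% | 99% | 26% |

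**Sensitivity to the borrowed effect.** At 0.10 SD and ρ = 0.5 the noncentrality is 0.10/0.25 = 0.4 times as large (1.14 and 1.41), and power moves only from about 21% to 29%. The variance cut does not depend on the effect size.

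**12 months.** The same formulas with weights 0.0417, 0.25, 0.4583 and 0.25 give variance cuts of 16%, 34% and 56%. No 12-month power is given, because 233 is the 6-month number and the SAP states no 12-month attrition.

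**The case against.** *The promised adjusted means may already include baseline EQ-5D.* Possibly, and a reader should not infer that the SAP rules such adjustment out. But severity is the only adjustment variable that it names. If baseline utility was intended, the SAP should say so; otherwise the choice is left until the data are seen.

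*Randomisation protects the comparison.* This stands. A reader might infer that the planned QALY comparison is biased or its interval wrong. The documents do not support that: patients are individually randomised, the estimate is unbiased over randomisations, and an interval without the covariate already allows for chance imbalance. Nor does the whole of an imbalance carry over; only the fraction worked out above does.

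*The SAP gives no QALY formula, and the template includes change from baseline.* This also stands, and the size and direction depend on it. If the area were taken relative to baseline utility, the slope at ρ = 0.5 would be 0.271 − 0.5 = −0.229. The carry-over would reverse sign, at about 0.229 × 0.866 × 0.0926 / 0.1057 = 17% of the same assumed effect. Imbalance would still enter. With baseline utility as a covariate, both constructions give the same group difference, because subtracting a multiple of the covariate changes only its own coefficient.

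*A protocol or health-economic plan may cover this.* The abbreviations list contains ICER and CEAC, which the body never uses, and section 1 says that the protocol already describes some methods. That is suggestive, but no such text is shown. The point also does not rest on silence: 5.2.2 states a model for QALYs, and that model can be improved.

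*It is one of many secondary outcomes, and the trial was not sized for it.* True. That limits the priority, not the case for a change this cheap.

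**Conclusion.** The point holds as an improvement in efficiency and in protection against realised imbalance, not as an error of validity. The stated QALY model contains group and the severity stratum but not baseline EQ-5D utility. Under the assumptions listed above, adding it cuts residual 6-month QALY variance by about 17% to 57% and removes a carry-over of about 15% to 26% of the assumed effect per one-standard-error imbalance.

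The variance cut is the firmest of these figures, since it needs only the utility correlations and the trapezoid form. The power and carry-over figures also depend on an effect borrowed from another instrument and should be read as illustrations. The change should be made, but nothing in the planned sample size or the primary analysis depends on it.

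**What to change.** In section 5.2.2, state that QALYs, calculated as the area under the EQ-5D utility curve from baseline to 6 and to 12 months, are compared between arms in a linear mixed model. Its fixed effects are group, depression severity stratum and baseline EQ-5D utility, and its random effect is GP practice nested in centre. A patient random effect is not needed, because each patient has one QALY value per horizon. Say that this adjusted difference is the one used in any cost-efficiency statement.

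The cost is one sentence and one covariate that is already collected, with no extra patients. The downside is that missing baseline EQ-5D must be handled within this QALY analysis. Section 5.3 plans multiple imputation of baseline variables only as a sensitivity analysis, so it does not cover the main QALY model as it stands.

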#### 5.2.3 Additional analysis

As additional exploratory analyses, subgroup analyses based on several demographic and clinical values are conducted w.r.t. change of PHQ-9 score. The aim of these analyses is to identify subpopulations, which benefit more or less from the intervention. These analyses shall give a first starting point for future studies. Missing values will not be imputed, but the implicit MAR assumption of the analysis model will be used.

The presented p-values are of descriptive nature only (two-sided tests at unadjusted significance level of 5%). The analyses are conducted in the FAS.

For the analyses on a potential interaction between the intervention and age (continuous, and categorical: young [ $\leq$ first tercile] vs. old [ $>$ third tercile]), sex (men vs. woman), depression history (previous episode vs. no history of depression), other mental health comorbidity (mental health comorbidity vs. mental health comorbidity), city size (ordinal), education ( $\leq$  10 years in school vs.  $>$  10 years in school), living situation (living together vs. alone), insurance status (private vs. statutory health insurance), reason for GP visit (psychological vs. physical), migration background (migration background vs. no migration background), quality of life at baseline (continuous and dichotomized with median as cut-off point; based on the visual analogue scale of the EQ-5D), anxiety disorder (yes vs. no), substance disorder (yes vs. no), chronic physical disease (yes vs. no), persistent somatic symptoms (yes vs. no), mood swings (yes vs. no), social support (yes vs no), pregnancy in female patients (yes vs. no) and breast feeding in female patients (yes vs. no) on the change in PHQ-9 score from baseline to month 6, the regression models and their parameters are defined analogously to the primary analyses but additional effects for demographic and clinical values and its interaction with the treatment are added to each model.

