### 2.3 Sample size

The sample size calculation is based on the results of the preliminary study called DEPSCREEN-INFO, which showed an effect of Cohen's  $d = 0.27$ . In this study a lower effect of  $d = 0.25$  for the intervention group compared to the other groups is supposed. The sample size was calculated for an ANOVA based on the F-test. Because of the closed test principle, in case of a significant result in this overall test, the pairwise comparisons can be performed without adjustment of the type-I error. To detect the underlying effect size through an F-test with a significance level of  $\alpha = 0.05$ , a power of  $1-\beta = 0.8$  and group effects 0 and 0.25 a sample size of  $n = 233$  is needed in every group (balanced design). This adds up to a total sample size for the actual enrolment of  $N = 699$  (computations were made with PASS 2008). The estimated prevalence of depressive disorders in a GP's office is 15%. 50% of all participants of the depression screening are not going to be eligible to further participate in the study as they achieve a lower PHQ-9 score than 10. Based on previous work a loss of 35% of included patients at the time of the 6-months follow-up is expected. Therefore, 1074 patients have to be included in the study in order to roughly maintain 699 patients for the primary analysis. Five study centres with each 10 GP's offices therefore have to include at least 14320 patients in the study. Thus, in every GP's office 287 patients (rounded from 286.4) will be screened on average. 30 patients will be asked to participate at each GP's office per day whereas only 15 of them consent and are eligible for the study. The total recruitment length then adds up to  $14350 / (15*5) = 192$  recruitment days if patients will be recruited simultaneously in all 5 centres. Considering weekends leads to  $192 * (7/5) = 269$  days or 39 weeks of recruitment. To take unforeseen recruitment problems into consideration the total length is extended to 12 months.

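### The categorical age subgroup places old patients above the third tercile, where no patient can be, so that interaction cannot be estimated as written

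*SAP*

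**What the plan says.** SAP section 5.2.3 introduces the subgroup work with "As additional exploratory analyses, subgroup analyses based on several demographic and clinical values are conducted w.r.t. change of PHQ-9 score". Age is the first modifier listed, and it is to be used in two forms: "For the analyses on a potential interaction between the intervention and age (continuous, and categorical: young" opens a bracket that goes on to define young as at or below the "first tercile] vs. old [ $>$ third tercile". The model for each modifier is the primary one, to which "additional effects for demographic and clinical values and its interaction with the treatment are added to each model". The outcome is the change in PHQ-9 from baseline to month 6.

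On the status of the results, the section says "The presented p-values are of descriptive nature only (two-sided tests at unadjusted significance level of 5" per cent).

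The SAP does not define tercile elsewhere, and it does not say what happens to patients who are neither young nor old. Later in the same list, the item on other mental health comorbidity gives its two levels as "mental health comorbidity vs. mental health comorbidity".

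**The concern.** The rule for young uses a tercile as a cut-point: a patient counts as young at or below it. Carried through to the other end, the third such cut-point is the highest age in the sample. A rule that asks for patients above it selects nobody.

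An analyst who codes the rule as written gets a contrast with one empty side and no treatment-by-age-group interaction. Someone then has to decide what was meant. If the upper third was meant, the middle third belongs to neither group, and the SAP does not say whether this is intended. The version history records version 1.2 as a change to section 5.2.3 that added a prespecified subgroup, so a definition in this section ought to be one that can be run.

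**Working it through.** **Inputs.** From section 5.2.3: the two age rules, the continuous form, and the interaction model. From section 2.3: three arms, 233 per arm, and "1074 patients have to be included in the study in order to roughly maintain 699 patients for the primary analysis". The SAP gives no age distribution, so ages were simulated in three assumed shapes (continuous, whole years, skewed). The main result does not depend on them.

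**1. The plan's own figure.** The age subgroup has no stated figure. The sample size, needed here only for the patient numbers, reproduces. It is stated for an F-test at 5% with 80% power "and group effects 0 and 0.25 a sample size of" 233 per group.
- Standardised means 0, 0 and 0.25 have mean 0.0833. The noncentrality is n × Σ(μ − mean)² = n × 0.04167, or 9.71 at n = 233.
- Power is 0.801 at n = 233 and 0.7996 at n = 232, so 233 is right and 3 × 233 = 699.
- With 35% loss, 1074 × 0.65 = 698.1, in line with roughly 699.

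**2. Who is above the third tercile?** There are three ways to read the term.
- As a cut-point, it is the 3/3 quantile, the sample maximum. The count above a maximum is 0.
- As a group, it is the top third. No patient lies above the top third.
- If only the two inner cut-points are called terciles, there is no third one.

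No reading gives a non-empty group. The simulated samples illustrate this:

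| Patients | Young (≤ 1/3 quantile) | Above 3/3 quantile | Above 2/3 quantile | Between the 1/3 and 2/3 quantiles |
|---|---|---|---|---|
| 699 | 233–234 | 0 | 222–233 | 233–243 |
| 1074 | 358–359 | 0 | 344–358 | 358–371 |

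The ranges come from tied ages when age is in whole years.

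**3. Can the interaction be estimated?** The fixed part needed for the interaction has six columns: intercept, two for treatment group, one for age, and two for age by treatment.
- Categorical as written: the age indicator is 0 for everyone, so the age column and both interaction columns are all zeros. The rank is 3 of 6, and the age term and both interaction terms are not estimable.
- Categorical with old above the 2/3 quantile: rank 6 of 6, estimable.
- Continuous age: rank 6 of 6, estimable.

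**4. Size of the groups once corrected.** A third of 699 is 233, which happens to equal the number per arm but is a different group. Per arm that is 699 / 9, about 78 patients in each age third. A contrast of lower against upper third uses about 466 of 699 and leaves out about 233. On all 1074 included patients, each third would be about 358. The smaller base is the relevant one for patients with a 6-month outcome.

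**5. The comorbidity item.** Both sides carry the same label, so no contrast is defined literally. Depression history and migration background in the same list each set presence against absence, which shows what was intended.

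**The case against.** The intended meaning is easy to see. Terciles fix the cuts at the 1/3 and 2/3 quantiles, and with young as the lowest third, old can only sensibly be the highest third. That stands, and it is why the correction is small. It does not make the written rule correct.

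A reader might infer that the trial's age interaction as a whole cannot be estimated. The SAP does not support this: the same bracket also plans age as a continuous variable, which uses every patient and is estimable.

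A reader might also infer that prespecification is defeated because a cut must be chosen after seeing the data. That goes too far. The cut can be fixed from the ages alone without any outcome data, and the wording leaves little room for choice.

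Leaving out the middle third is not an error in itself. Comparing the extreme thirds is a recognised contrast, and the continuous form covers everyone. The only gap is that the SAP does not say so.

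The comorbidity item is plainly a dropped negation that no analyst would code literally. It carries no weight of its own and is included only because the same edit can correct it.

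**Conclusion.** The point holds for the categorical form of age only. As written, the old group has 0 patients for any age distribution, and the young-versus-old by treatment interaction is not estimable (rank 3 of 6). This assumes that the terciles are taken from the trial's own patients.

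The consequence is minor. It affects one of two forms of one modifier in a list of 19, in an exploratory analysis with descriptive p-values. The continuous age interaction, the primary analysis, the sample size and the control of type I error are untouched. The figure of about 233 old patients after correction rests on the SAP's expectation of 699 patients at 6 months. Tied ages brought it down to 222 in the simulated whole-year ages.

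**What to change.** In SAP section 5.2.3:

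- Define old as above the second tercile cut-point (the 2/3 quantile of age), and keep young as at or below the first.
- State that the middle third is left out of this contrast, if a comparison of the extreme thirds is intended.
- Write the comorbidity contrast as mental health comorbidity versus no mental health comorbidity.

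This changes wording only and needs no new data. A three-level age factor (lower, middle, upper third) would keep all patients in the categorical analysis. With three arms it raises the interaction from 2 to 4 degrees of freedom. It is an optional alternative and is not needed to correct the error.
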